2.8.1.2 Feasibility analysis

Table 7. Measures and analysis for feasibility, acceptability, and effects on engagement in care

Assessment	Assessment methods	Timing	Statistical test
Feasibility and Acceptability			
Trial: Feasibility	Proportion of enrolled participants among approached and eligible patients	base-line	Proportion, total study
	Proportion of participants with complete follow-up	1 year	
Intervention: Feasibility	Proportion of planned home visits successfully completed, patient-centered counseling sessions completed, medical assessments, medication reconciliations, and food security management	3 m	Proportion, Home Link Arm
Acceptability	Acceptability questionnaires with 7 acceptability domains for HCWs and participants	6 m	Proportion, Home Link arm
Acceptability	In depth interviews	6 m	Thematic analysis
Effects on care engagement barriers			
Cost of care access	Structured questionnaire for participant self-report	3 m, 6m	Wilcoxon rank sum
Medication reconciliation	Reconciling planned meds on discharged actual meds with patient & way that patient is taking	3 m	Proportion, Home Link arm
HIV stigma	Short form HIV stigma scale ^{45,46}	baseline, 6 months	Wilcoxon rank sum test
Social Support	MOS social support instrument ⁴⁷	baseline, 6 months	Wilcoxon rank sum test
Food security	Three question scale	baseline, 6 months	Wilcoxon rank sum test
Depression	CES-D (short)	Baseline, 6 months	Proportion

Alcohol use	Alcohol use disorder identification test (AUDIT), shortened version	Baseline, 6 months	Proportion
-------------	---	--------------------	------------

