2.7.4.3 Effect of intervention on barriers to care engagement

We will compare, by study arm, constructs anticipated to be effected by the intervention: care access, burden of treatment including cost to the patient and time spent by the patient, patient satisfaction, correct medication administration, internalized and experienced HIV stigma, social support, and food security (Table 5).

Time spent and patient-level financial cost of care will be ascertained by participant self-report using a field team member administered questionnaire with questions focusing on the last clinical contact (clinic or household visit) since hospital discharge, the total number of contacts (visits), the cost of transport and incidental expenses with going to the clinic and lost wages. Specific cost characteristics (such as transport cost and date of clinical care visit) will be verified using objective measures such as local mini-bus fares and medical file abstraction (at 26 weeks after discharge).

Table 5. Measures and analysis for feasibility, acceptability, and effects on engagement in care

Assessment	Assessment methods	Timing	Statistical test	
			Feasibility and Acceptability	
Trial: Feasibility	Proportion of enrolled participants among approached and eligible patients Proportion of participants with complete follow-up	base-line 1 year	Proportion, total study	

Intervention: Feasibility	Proportion of planned home visits successfully completed, patient-centered counseling sessions completed, medical assessments, medication reconciliations, and food security management	3 m	Proportion, Home Link arm
Acceptability	Acceptability questionnaires with 7 acceptability domains for HCWs and participants	3 m	Proportion, Home Link arm
Acceptability	In depth interviews	3 m	Thematic analysis
Effects on care engagement barriers			
Patient cost	Structured questionnaire for participant self-report	3 m, 6m	Wilcoxon rank sum
Care satisfaction	Adapted South African care satisfaction survey ⁴⁴	3 m	Wilcoxon rank sum test
Medication reconciliation	Reconciling planned meds on discharged actual meds with patient & way that patient is taking	3 m	Proportion, Home Link arm
HIV stigma	Short form HIV stigma scale ^{45,46}	baseline, 6 months	Wilcoxon rank sum test
Social Support	MOS social support instrument ⁴⁷	baseline, 6 months	Wilcoxon rank sum test
Food security	Three question scale	baseline, 6 months	Wilcoxon rank sum test
Depression	CES-D (short)	Baseline, 6 months	Proportion

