Alcohol use	Alcohol use disorder identification test (AUDIT), shortened version	Baseline, 6 months	Proportion

Medical conditions and psychosocial needs will be assessed prior to hospital discharge and post-hospital by using Home Link visit and other care contact records.

a. Medical assessment prior to hospital discharge: Clinical data will be abstracted or specifically obtained for the study, if not in the clinical record: HIV viral load, CD4 count, HIV drug resistance testing, Xpert Ultra for rapid TB diagnosis, discharge diagnoses, and discharge medications.

Blood will be drawn from all participants living with HIV for drug resistance testing; however, we will only conduct the drug resistance test if the viral load result is >1000 copies/mL. We may use leftover specimen from the drug resistance test to repeat the viral load and drug resistance test using a plasma separation card in collaboration with the National Institute for Communicable Diseases (NICD).

b. Psychosocial assessment prior to hospital discharge: social support, depression, economic status, and HIV stigma will be measured. The 12-item HIV stigma scale⁴⁵ (including enacted, internalized, and anticipated stigma components), CES-D (short) depression scale, MOS social support instrument, food security, and AUDIT alcohol use instrument will be administered to participants prior to discharge (E002).

c. Post-hospital services delivered: All post-hospital assessments (Home Link visit clinical instrument (HL001), participant challenges identified during patient-centered counseling sessions (from structured counselor notes), triage decisions from the discharge officer, findings on laboratory testing, and clinical evaluation during inpatient or ambulatory care that Home Link arm participants receive will be abstracted from hospital or clinic paper or electronic records and

the electronic National Health Laboratory Service records. These data will be organized to describe the intensity of care, psychosocial needs, clinical decision making, and most common clinical scenarios.

Sampling: All participants will have in-hospital laboratory and psychosocial assessments. All participants in the Home Link arm will be included in the assessment of post-discharge needs and triage outcomes.

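### Stigma, social support and food security are compared by a rank sum test with no baseline term, although baseline scores are collected and adjusting for them would be more precise

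*Combined protocol and SAP*

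**What the plan says.** The second primary objective (Section 1.2) covers the effect of Home Link on barriers to care. Section 2.7.4.3 turns this into a between-arm comparison: "We will compare, by study arm, constructs anticipated to be effected by the intervention". Stigma, social support and food security are on the list that follows.

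Table 5 (Section 2.7.4.3) and Table 7 (Section 2.8.1.2) name the instruments as "Short form HIV stigma scale", "MOS social support instrument" and "Three question scale". All three are timed at "baseline, 6 months", and the analysis entry for each is "Wilcoxon rank sum test" and nothing more.

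The baseline values will exist. Section 2.7.4.3, item b, puts the stigma scale on form E002 and continues: "CES-D (short) depression scale, MOS social support instrument, food security, and AUDIT alcohol use instrument will be administered to participants prior to discharge". Table 10 (Section 3.3) schedules E002 again at 26 weeks.

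For these scales the plan does not state:
- whether the six-month score or the change from baseline is ranked;
- any baseline covariate, or use of the HIV-status stratum from the randomization;
- how deaths and missing six-month scores are handled.

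The one covariate model in the plan, the logistic regression in Section 2.8.1.4, relates post-hospital outcomes to in-hospital measures. It is not assigned to these comparisons.

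**The concern.** A rank sum test on six-month scores makes no use of a baseline measurement that the trial has already paid for. In a pilot whose size was set by time and budget, that is precision given away on part of a primary objective. A rank sum p-value also gives the later full trial no adjusted effect estimate with an interval.

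A second, weaker issue is that a six-month score needs a participant who is alive and reached at 26 weeks. If mortality differs by arm, the groups compared are no longer the randomized groups, and the plan does not say how the result should be labelled or read.

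**Working it through.** **1. The plan's own figure.** The plan gives no power, SD or correlation for these scales. Its only calculation is mortality power in Table 9 (Section 3.2): 26% vs 10%, 90 people with HIV (PWH) per arm, alpha 0.05, power .803. With a two-sided pooled chi-square test:
- pooled SE = √(2 × 0.18 × 0.82 / 90) = 0.0573
- unpooled SE = √((0.26 × 0.74 + 0.10 × 0.90) / 90) = 0.0560
- power = Φ((0.16 − 1.96 × 0.0573) / 0.0560) = Φ(0.85) = 0.803

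All seven rows reproduce to within 0.002. The text of Section 3.2 speaks of 120 split 1:1, but 60 per arm gives 0.63, so I use 90.

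**2. Expected survivors at that effect.** 90 × 0.74 = 66.6 (care as usual) and 90 × 0.90 = 81 (Home Link).

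**3. Gain from adjustment.** Let r be the baseline-to-six-month correlation. It is not in the documents; I take 0.3, 0.5 and 0.7. With equal variance at both times, relative to an unadjusted six-month comparison:
- adjusted residual variance: 1 − r² = 0.91 / 0.75 / 0.51
- equivalent extra patients: 1/(1 − r²) − 1 = 10% / 33% / 96%
- change-score variance: 2 − 2r = 1.4 / 1.0 / 0.6

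Since (2 − 2r) − (1 − r²) = (1 − r)² ≥ 0, a change score is never more precise than adjustment.

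**4. Smallest detectable difference** (80% power, SD units) = (1.960 + 0.842) × √((1/n₁ + 1/n₂) × V). V is π/3 for rank sum on normal six-month scores, (π/3)(2 − 2r) for rank sum on change, and 1 − r² for adjusted regression.

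| Scored per arm | Rank sum, six-month | Rank sum, change (r = 0.3 / 0.5 / 0.7) | Adjusted (r = 0.3 / 0.5 / 0.7) |
|---|---|---|---|
| PWH, 66.6 vs 81 | 0.47 | 0.56 / 0.47 / 0.37 | 0.44 / 0.40 / 0.33 |
| PWH, 75% of survivors reached | 0.55 | 0.65 / 0.55 / 0.42 | 0.51 / 0.46 / 0.38 |
| All, 88.8 vs 108 | 0.41 | 0.49 / 0.41 / 0.32 | 0.38 / 0.35 / 0.29 |

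The second row applies the 75% follow-up target of Section 2.7.4.1 to survivors, which is my assumption. The third assumes the same mortality in HIV-uninfected participants, for whom the plan gives no rate. In the first row about 0.01 SD of each drop from 0.47 comes from leaving ranks under normality: 0.474 × (1 − 1/√(π/3)) = 0.011. The 10% / 33% / 96% figures exclude this.

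**5. Selection by survival.** Suppose patients saved by Home Link score g SD worse than other survivors. The shift in the Home Link mean is (difference in mortality) × g / (Home Link survival). With g = 0.5 (assumed):
- 26% vs 10%: 0.16 × 0.5 / 0.90 = 0.09 SD
- 26% vs 20%: 0.06 × 0.5 / 0.80 = 0.04 SD
- equal mortality: 0

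A simulation of 3,000 trials per setting, with 90 per arm, mortality 26% vs 10% and no true effect on the score, gave:
- Baseline score raises the odds of death 1.5- to 2-fold per SD: unadjusted bias 0.02 to 0.07 SD against a standard error near 0.165 SD, adjusted bias about 0, rank-sum type I error 4.9% to 6.6%.
- An unmeasured factor of equal strength (2-fold) also drives death and score, r = 0.5: bias 0.09 SD unadjusted and 0.05 SD adjusted, rank-sum type I error 8.2%.
- Equal mortality: no bias.

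**The case against.** The best defence is that a rank test is a reasonable choice for short ordinal scales. These are secondary measures in a pilot, no power is claimed for them, and Section 3.2 puts feasibility and acceptability first. Baseline is taken during an acute admission, so r may be low; at r = 0.3 the detectable difference moves only from 0.47 to 0.44 SD. All of this stands and keeps the point minor. It does not make the rank test preferable, because proportional-odds regression respects ordinal scales and also uses the baseline.

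Adjustment has a cost of its own. Section 2.3.1 allows consent by next of kin for patients lacking capacity, so some participants may have no usable baseline E002. A complete-case regression could drop the sickest, so a missing-baseline rule is needed.

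Two stronger readings are tempting, and the documents support neither:

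- A reader might infer that the planned test cannot use the baseline score. A rank sum test can be run on changes, and the timing entry leaves that open. What holds is that the plan does not say, and that adjusted regression is more precise than either version at the correlations considered.
- A reader might infer that survival tilts the comparison against Home Link and that adjustment corrects it. Nothing in the documents says that patients who would have died under usual care score worse on these scales. The 0.09 SD needs both an assumed 0.5 SD deficit and the one mortality gap for which the plan claims adequate power. If changes are ranked and baseline score drives death, the bias is (r − 1) rather than r times the baseline imbalance, so its sign reverses. Adjustment removes only what measured baseline explains.

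**Conclusion.** The point holds as a low-cost improvement in precision. Naming baseline-adjusted regression is worth about 10%, 33% or 96% more patients than an unadjusted six-month comparison at assumed r of 0.3, 0.5 or 0.7, and the ordering against a change-score analysis does not depend on r. The figures assume equal variance at both times and roughly normal scores.

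Selection by survival is a matter of labelling and reporting. It is likely small (zero at equal mortality, about 0.04 to 0.09 SD across the two mortality gaps in step 5 with the assumed deficit), its direction is uncertain, and adjustment only partly removes it.

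**What to change.** In Tables 5 and 7, for stigma, social support and food security:

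- Make the between-arm analysis a regression of the six-month score on arm, adjusted for the baseline score, age, sex and HIV status. Use a linear model, or proportional odds for short ordinal scales. Report the adjusted difference or odds ratio with its 95% confidence interval.
- For stigma, analyse PWH only and omit HIV status, which is constant in that group.
- State a simple rule that keeps participants with a missing baseline score, for example mean imputation with a missing indicator.
- Keep the rank sum test as a sensitivity analysis if wanted, and state what is ranked.
- Label each result as among survivors with a six-month score, and show deaths and other missing scores by arm beside it.

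No new visit, form or measurement is needed. The cost is analysis wording, ordinary model assumptions and the missing-baseline rule.

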- (a) Assess illness severity. The nurse will assess for symptoms of COVID-19 infection and active TB disease as well as general illness severity using temperature, blood pressure, pulse, respiration rate, pulse oximetry, and orientation. Use of these signs will be guided by an algorithm (Appendix A) leading to (i) discharge from home visits, (ii) return visit in 2 weeks, (iii) contacting a clinician at Tshepong Hospital via cellphone for further guidance, or (iv) calling for routine medical transport (ambulance service) to transport the participant to Tshepong Hospital for evaluation and likely admission.
- (b) Medication reconciliation: review medication taking, medication availability, and prescribed medication plan. Counsel on appropriate dosing and address potential adherence barriers (e.g. lack of understanding, lack of medication availability, nausea or other side effects).
- (c) Obtain laboratory specimens (whole blood or urine, as required based on the discharge officer assessments) for transport to the laboratory and provide medications dispensed for the patient from the Tshepong Hospital pharmacy as indicated for a given participant.
- (d) Distribute any medications needed based on prescription from the discharge officer (based on a prior household visit assessment).

Primarily provided by counselor

- (e) Household assessment: assess for food availability and home support; (involve social workers at Tshepong Hospital if indicated) (completed during medical assessment).
- (f) Patient-centered counseling to address readiness for treatment engagement including readiness to accept treatment, readiness to face stigma and disclosure needs, building self-efficacy for care engagement, and providing counseling for symptoms of depression and/or alcohol abuse identified prior to hospital discharge or during home visits.
- (g) Participants who have low food security identified prior to hospital discharge will be provided with a food supplement/parcel at the first home visit.

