2.7.4 Acceptability & Feasibility

2.7.4.1 Feasibility of Home Link

The goal of this assessment is to evaluate the feasibility of implementing the Home Link intervention and of endpoint ascertainment for the clinical trial of Home Link implementation.

Specific feasibility considerations are:

- 1) The proportion of participants in the Home Link arm who receive each scheduled/expected Home Link home visits
- 2) Success of the study team to ascertain six month mortality

We will assess the trial feasibility based on the proportion of eligible individuals who enroll and the proportion of participants that we are able to collect full outcome data on. We will assess the feasibility of implementing the intervention on the following measures: the proportion of planned home visits that are completed, the proportion of home medical assessments completed, the proportion of home medication reconciliation completed, the proportion of participants who receive patient-centered counseling, and the proportion of participants with identified food insecurity who receive food supplementation/parcels at the first home visit. The proportions will be considered individually and with a composite score to be interpreted in the context of the efficacy results with a general threshold that substantially more than half of components expected to be completed need to be completed for the intervention to be considered feasible.

Success will be based on *a priori* targets of $\geq 90\%$ of planned home visits completed, successful follow-up of $\geq 75\%$ of participants, and vital status ascertainment of $>90\%$ of participants.

Table 4. Feasibility Indicators

Numerator	Denominator	Measure
-----------	-------------	---------

Number with first Home Link visit	Total in Home Link arm	Proportion
Number of completed Home Link visits	Number of planned/attempted Home Link visits	Proportion
Number of home medical assessments completed	Number of planned/attempted/completed Home Link visits	Proportion
Number of home medication reconciliation completed	Number of planned/attempted/completed Home Link visits	Proportion
Number of patient-centered counseling sessions completed	Number of planned/attempted/completed Home Link visits	Proportion
Number of participants who received food parcels	Number of Home Link participants with identified food insecurity pre-discharge	Proportion
Number of participants with 6 month vital status ascertainment	All study participants	Proportion

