3.2 Study sample size justification

We propose to recruit a sample of 240 participants randomized 1:1 into care as usual and Care Link arms. The participants will be blocked to include 30 HIV-uninfected adults and 90 people living with HIV per arm. The sample size has been determined to be feasible given time and budget limitations while still providing insight into the efficacy. Using the base rate of mortality from our preliminary study of 26% and an alpha of 0.05 and a sample size of 120 split 1:1 in care as usual and Home Link arms we have represented power versus intervention arm mortality, with sub-group analysis limited to PWH, in Table 11. We note that the primary goal is feasibility and acceptability. We are appropriately powered only for a substantial decrease in mortality from 26% to 10%.

Table 9. Power by varying effect size on reducing post-hospital mortality

alpha	power	N	N1	N2	delta	p1	p2
.05	.1589	180	90	90	-.06	.26	.2
.05	.2527	180	90	90	-.08	.26	.18
.05	.3764	180	90	90	-.1	.26	.16
.05	.5212	180	90	90	-.12	.26	.14
.05	.6704	180	90	90	-.14	.26	.12
.05	.803	180	90	90	-.16	.26	.1
.05	.9019	180	90	90	-.18	.26	.08

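### Depression and alcohol use, both counselled on by Home Link, have no between-arm analysis or cut-off specified; for depression, a yes/no comparison would also lose power against the score

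*Combined protocol and SAP*

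**What the plan says.** Section 1.2 makes the effect of Home Link on barriers to care part of primary objective 2. Section 2.5.2, item (f), includes in the home counselling "providing counseling for symptoms of depression and/or alcohol abuse identified prior to hospital discharge or during home visits".

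Section 2.7.4.3 states: "We will compare, by study arm, constructs anticipated to be effected by the intervention". The list that follows runs from care access to food security. It does not name depression or alcohol use, but it ends by citing Table 5.

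Table 5, and Table 7 in section 2.8.1.2, contain both constructs in the block on effects on barriers, measured at baseline and 6 months. The alcohol instrument is given as "Alcohol use disorder identification test (AUDIT), shortened version". For both rows the test column reads only *Proportion*. HIV stigma, social support and food security, on the same schedule, are each given "Wilcoxon rank sum test".

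Section 3.1 (Table 8) has E002, which holds both scales, collected in both arms in hospital and after discharge. Section 3.3 (Table 10) places the later collection at 26 weeks.

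**The concern.** Two conditions that the counselling addresses are measured before and after in both arms, yet the plan does not say how the arms will be compared on them. The analyst would have to decide, with the data in view, whether to compare at all, what test to use and where to cut each scale. No analysis cut-off is given anywhere. Section 4 mentions thresholds only for clinical referral, and without numbers.

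If *Proportion* means the share above a cut-off, the depression score would be reduced to yes/no and the information within each category would be lost. The pilot is meant to lead to a protocol for a full trial, so a between-arm estimate with an interval for each counselling target is worth having, and the data are already being collected.

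**Working it through.** **What *Proportion* can mean.** Two features suggest that no comparison was written down. Where the plan intends a test of two proportions it names chi-square (Tables 3 and 6), and the other *Proportion* entries in Tables 5 and 7 are single-group summaries. One feature points the other way: those other entries are restricted to the Home Link arm or the whole study, while the depression and alcohol rows have no restriction. The logistic models in section 2.8.1.4 include trial arm, but they use in-hospital psychosocial measures as predictors and do not name 6-month CES-D or AUDIT as outcomes. The text does not settle the question.

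**Plan's own power figure.** None is given for these outcomes. The only stated power is for mortality (Table 9), which serves to check the formula:

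power = Φ{[|p1 − p2|√n − 1.96√(2p̄(1 − p̄))] / √(p1(1 − p1) + p2(1 − p2))}

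With p1 = 0.26, p2 = 0.10, n = 90 and p̄ = 0.18: (1.518 − 1.065)/0.531 = 0.853, and Φ = 0.803. Table 9 states .803, so it is reproduced with two-sided alpha 0.05.

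**Inputs for depression.** The plan gives no SD, prevalence, cut-off or effect size, so all of these are assumed.
- Number per arm: 120 × 0.82 alive × 0.90 reached = 88.6, taken as 88. The 0.82 and 0.90 are assumptions.
- Range from the plan's figures: the 75% follow-up target gives 120 × 0.75 = 90. Removing a further 26% for deaths gives 90 × 0.74 = 66.6, taken as 67.
- Normal score, shift of d SD in every Home Link participant, share p above the cut in care as usual.

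**Score.** Power ≈ Φ(d√(n/2) − 1.96). For d = 0.4, n = 88: Φ(2.653 − 1.960) = 0.756. The exact t calculation gives 0.751.

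**Yes/no.** The cut is c = Φ⁻¹(1 − p), and the Home Link share above it is 1 − Φ(c + d). For p = 0.35, d = 0.4: c = 0.385 and the share is 1 − Φ(0.785) = 0.216. The Table 9 formula with n = 88 gives 0.50.

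| n per arm, d | Score (t-test) | Yes/no, p = 0.50 | p = 0.35 | p = 0.20 |
|---|---|---|---|---|
| 88, 0.4 | 0.75 | 0.55 | 0.50 | 0.40 |
| 88, 0.5 | 0.91 | 0.74 | 0.68 | 0.55 |
| 67, 0.4 | 0.63 | 0.44 | 0.40 | 0.32 |

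The efficiency of the cut relative to the t-test is φ(c)²/[p(1 − p)]: 0.64 at p = 0.50 and 0.49 at p = 0.20.

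**Skewed depression score** (simulated; assumed gamma, mean 9, SD 5.5, 25% reduction, cuts 8 to 15, 90 per arm): Wilcoxon 0.82 to 0.83, yes/no 0.60 to 0.71.

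**Benefit only in those above the cut at baseline** (simulated; 88 per arm, normal scores, baseline-to-6-month correlation 0.5 to 0.7). With 35% above the cut and a 1.0 SD effect in them, power is 0.65 to 0.70 for the unadjusted score, 0.71 to 0.85 for the baseline-adjusted score, and about 0.53 to 0.68 for yes/no. In every normal-score setting tried, the adjusted score matched or beat yes/no. Part of that advantage comes from using the baseline, not only from keeping the score.

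**Alcohol** (simulated; assumed 50 to 70% non-drinkers, effect only in drinkers, cut at 4, 90 per arm): Wilcoxon 0.09 to 0.54, yes/no 0.17 to 0.76. The order reverses.

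**The case against.** The strongest reply is that the comparison is already planned. The by-arm sentence cites Table 5, both rows are in it, and their *Proportion* entry is not limited to one arm. This stands to the extent that a reader might infer the plan has decided against comparing the arms, and the documents do not support that. Proportions by arm could be reported from the plan as written, so it also goes too far to say that the pilot cannot tell whether these conditions changed. What remains is that no contrast, test or cut-off is named and the prose list leaves both constructs out.

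The second reply concerns size. Counselling on these conditions goes to participants with identified symptoms, and section 4 refers care-as-usual participants with positive pre-discharge screens too, so a 0.4 SD shift in everyone may be optimistic. This stands. With 35% above the cut and a 0.5 SD effect confined to them, power is about 0.20 to 0.22 for the unadjusted score and 0.19 to 0.22 for yes/no. With 20% above and a 1.0 SD effect, it is 0.27 to 0.29 against 0.22 to 0.35. The case for the score then depends on adjusting for baseline.

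Third, section 3.2 puts feasibility and acceptability first, and neither construct is among the effectiveness outcomes in Table 6. This also stands and limits the weight of the point. It does not remove the need to say what will be done with data collected under a primary objective.

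**Conclusion.** The point holds as an unspecified analysis for both constructs. For depression there is also a conditional loss of power: about 0.40 to 0.55 for a yes/no comparison against 0.75 for the score, with 88 per arm, a normal score, a 0.4 SD shift in everyone and 20 to 50% above the cut. All of these inputs are assumed. If only symptomatic participants benefit, the gap narrows and can vanish against an unadjusted score, but the baseline-adjusted score did at least as well as yes/no in the normal-score settings tried.

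Two stronger readings should be resisted. A reader might infer that the scores will certainly be dichotomised. That is suggested by *Proportion* but not stated. A reader might also extend the power loss to alcohol use. With many non-drinkers a yes/no test can outperform a rank test, so no such loss is shown for AUDIT. These outcomes are exploratory, and the mortality power in Table 9 is untouched.

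**What to change.** In Tables 5 and 7:
- Depression row: difference between arms in 6-month CES-D score, adjusted for baseline score and HIV status, with 95% CI.
- Alcohol row: a between-arm estimate with 95% CI, adjusted for baseline AUDIT and HIV status, from a named model suited to many zeros.
- Keep the proportion above a cut-off stated in advance as a descriptive summary for each scale.

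In section 2.7.4.3, add both constructs to the by-arm list. State that the comparison is among survivors with a 6-month score and report it next to mortality by arm, because deaths before 6 months leave a selected group if mortality differs.

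The cost is analysis wording only, with no new data. The downside is two more exploratory comparisons, which should be labelled as such.
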